3.3 STRATEGIES FOR RECRUITMENT AND RETENTION

3.3.1 RECRUITMENT

The target population of this study includes healthy individuals between the ages of 18 to 35 recruited from UNC Chapel Hill and the surrounding area, including approximately 30,000 candidates for participation. Recruitment will occur via two methods: flyers to be distributed at major locations on the campus (libraries, gyms, classroom buildings, etc.) and a mass email to all individuals with a UNC-affiliated email address.

3.3.2 RETENTION

The retention strategy includes a payment schedule of four times per participant, corresponding with the four sessions. Payment is increased for each session to incentivize completion of the study. Individuals who complete both sessions will receive a non-coercive bonus payment, as well. Research staff will send participants a reminder text the day before each session, and will be available by email and phone at all times.

4 BASIC STUDY DESIGN

The design for this study is a pilot, randomized, double-blind, sham-controlled, crossover clinical trial which will be used to demonstrate feasibility and collect effectiveness data for further refinement of CF-tACS approach and for the subsequent design of a follow-up, multi-site, large scale study. We are seeking 24 healthy participants, both male and female, between the ages of 18-35. All women of child-bearing potential (defined as menstruating women of all ages) will be asked to take a pregnancy test during the initial session in order to determine eligibility for the study. We estimate 2 months to complete study enrollment.

The experimental design is a 3-treatment, 3-period, 3-sequence crossover with a 1 week washout interval between periods. N=24 participants will be enrolled and allocated by stratified randomization to six treatment sequences, S-At-Ad, S-Ad-At, At-S-Ad, At-Ad-S, Ad-S-At, Ad-At-S. S refers to Sham Regimen which is 40 minutes of sham CF-tACS, At refers to Active Theta-Gamma Frequency Regimen which is 40 minutes of verum CF-tACS, and Ad refers to Active Delta-Beta Frequency Regimen which is 40 minutes of verum CF-tACS.

Participants will be randomly assigned to one of 6 sequences on the first visit.

Sham treatment will include 10 seconds of ramp-in to 1 minute of CF-tACS with a ramp-out of 10 seconds for a total of 80 seconds of stimulation. The 80 seconds of stimulation serves to desensitize the scalp beyond which participants are generally not able to tell apart the presence or absence of stimulation. This strategy has been described in previous studies using tACS (Alekseichuk et al. 2017; Mellin et al. 2018). Verum CF-tACS will have a 10 second ramp-in and ramp-out with 5 minutes of stimulation, for 8 separate blocks with a minimum 3 minute break between each block, for a total of 2560 seconds of stimulation. Stimulation waveform is coupled frequency with a low frequency component and brief high frequency component on each cycle with maximum amplitude of 2 mA.

Eligible participants will have a total of 4 visits, each lasting approximately 3 hours and separated by at least 1 week. Total participation will include about 12 hours over the course of four weeks. All time estimates take into consideration breaks and time variance in administration.

4.1 TREATMENT ASSIGNMENT PROCEDURES

Participants will be randomized into one of 6 sequences. This is a double-blind study, so neither the participant nor the researcher will know which treatment the participant is receiving, if any.

4.1.1 RANDOMIZATION PROCEDURES

[name] will randomize 24 6-digit stimulation codes which will be used by the study coordinator and research assistants and will be linked to the participant numbers of enrolled participants. These stimulation codes are directly linked to which treatment participants receive (sham CF-tACS, theta-gamma verum CF-tACS, or delta-beta CF-tACS) at each session, and will be used with the NeuroConn stimulator. An unblinded code sheet that matches these stimulation codes to treatment arm will be kept by [name] and will not be available to the study coordinator or research assistants. [name] will not be involved in data collection, interaction with participants or data analysis ensuring double-blind.

The unblinded code sheet will have the following information:

- The initial identifier codes for all potential participants
- Stimulation code: 6-digit numerical code for the stimulation session

- Condition number: Numerical code for the condition
- Condition name: Name of the condition

A copy of this code sheet with condition number and condition name REMOVED is provided to the study coordinator and research assistants. This blinded code sheet will be used to ensure the correct stimulation code is provided for each session.

These linked codes ensure that the study coordinator and research assistants are kept blinded to which treatment each participant receives. Please see Data and Safety Monitoring for more information on unblinding this information.

4.1.2 DROPOUTS

In case of dropouts, defined as not completing the stimulation part of either visits, data will not be included in the final analysis and the stimulation codes will be reused for the next participants.

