7 STUDY OUTCOMES

7.1 PRIMARY OUTCOMES

The cognitive task will consist of 400 trials. The EEG recorded simultaneously with the task will be analyzed following an established preprocessing pipeline to remove artifacts related to eye movements, eye blinks, heart beats and muscle activity. The oscillation power and phase will be estimated using Morlet wavelet convolution. The primary outcome is phase-amplitude coupling between the stimulated frequencies (measured from EEG), reaction time, and accuracy. Phase amplitude coupling will be calculated using the phase locking value z-corrected based on a boot-strapped null distribution from randomly shifting the amplitude values 1000 times (see Cohen *Analyzing Neural Time Series Data* 2014 for method).

Our primary outcomes:

- Theta-gamma tACS will increase theta-gamma phase amplitude coupling (one-tailed, Student's t-test)
- Delta-beta tACS will increase delta-beta phase amplitude coupling (one-tailed, Student's t-test).
- Theta-gamma tACS will alter behavior (reaction time or accuracy) as a function of set-size (Student's t-test).
- Delta-beta tACS will alter behavior (reaction time or accuracy) as a function of abstraction (Student's t-test).

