7.2 SECONDARY OUTCOMES

The following will be assessed as secondary outcomes

- Brain behavior correlation to account for inter-participant variance. For the significant behavioral findings, we will correlate the strength of phase amplitude coupling during the post-stimulation rest period with the impact on behavior.
- For the significant behavioral findings, brain behavior correlation between the strength of phase amplitude coupling in the baseline session to the behavioral effect of CF-tACS on task performance.

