12.2 STATISTICAL ANALYSIS PLANS

Statistical analyses will be performed to test the null hypothesis indicated in section 2.4 *Study Aims/Hypothesis*.

The cognitive task will consist of 400 trials. The EEG recorded simultaneously with the task will be analyzed following an established preprocessing pipeline to remove artifacts related to eye movements, eye blinks, heart beats and muscle activity. The oscillation power and phase will be estimated using Morlet wavelet convolution. The primary outcome is phase-amplitude coupling between the stimulated frequencies (measured from EEG), reaction time, and accuracy. Phase amplitude coupling will be calculated as the phase locking value corrected for spurious noise using a boot-strapped null distribution (see Cohen Analyzing Neural Time Series Data 2014 for method).

Our primary outcomes and their test are described below:

- Theta-gamma tACS will increase theta-gamma phase amplitude coupling (one-tailed, Student's t-test)
- Delta-beta tACS will increase delta-beta phase amplitude coupling (one-tailed, Student's t-test).
- Theta-gamma tACS will alter behavior (reaction time or accuracy) as a function of set-size relative to sham-tACS (Student's t-test).
- Delta-beta tACS will alter behavior (reaction time or accuracy) as a function of abstraction relative to sham-tACS (Student's t-test).

As exploratory analysis, linear mixed-effects models with BDNF genotype, sex hormone levels, as factors in addition to the variables condition and period will be fit with the rest of the analysis following what is described for primary analysis.

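### Cheap improvement: people who do not complete stimulation are excluded and replaced, and the primary t-tests of this three-period crossover carry no period term, so the estimates describe completers only

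*Combined protocol and SAP*

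**What the plan says.** **Dropouts.** Under 4.1.2, a participant who does not complete stimulation is a dropout, whose "data will not be included in the final analysis and the stimulation codes will be reused for the next participants". Routes out include a missed session that cannot be made up (8.4), severe discomfort (9.2, 9.3), failure to keep to the rules, and the participant's own request (10.3.1). Safety data are collected on people discontinued for an adverse event, and each early withdrawal gets a note to file (10.3.2). Section 12.2 plans no account of withdrawals.

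**Primary tests.** The coupling tests take the form "Theta-gamma tACS will increase theta-gamma phase amplitude coupling (one-tailed, Student's t-test" (7.1). The behaviour tests in 12.2 are "as a function of set-size relative to sham-tACS (Student's t-test", with the delta-beta test worded likewise for abstraction. None has a period term. Period appears only in an exploratory mixed model, where genotype and hormone levels are factors "in addition to the variables condition and period will be fit with the rest of the analysis following what is described for primary analysis". No primary mixed model is described for it to follow.

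**Purpose.** Section 4 describes a sham-controlled crossover "which will be used to demonstrate feasibility and collect effectiveness data for further refinement of CF-tACS approach". Aim 3 in 2.4 is to obtain parameter estimates for planning a further study.

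**Number of stimulated sessions.** Section 6.2 and Appendix A give three, and 8.4 refers to the second, third and fourth sessions. The dropout definition in 4.1.2 is worded as if there were two visits, and 3.3.2 says: "Individuals who complete both sessions will receive a non-coercive bonus payment, as well".

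**The concern.** A pilot's main product is planning information. Three things weaken it here.

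1. Some exits can depend on the stimulation, because severe discomfort leads to withdrawal. Estimates from completers alone may then differ from those for everyone randomised, and the final analysis gives no view of the difference.
2. Someone who leaves after two stimulated sessions may already have given a sham and an active session. That within-person contrast is discarded.
3. If performance or coupling drifts across sessions, a t-test on the active-minus-sham difference counts the drift as noise. The test becomes conservative, and the SD carried into the next study is too large.

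**Working it through.** **Inputs from the documents.** N = 24 and six sequences (section 4); effect sizes 0.48 and 0.6, alpha 0.05, power above 60% and above 85% (12.3).

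**Assumptions, because the documents do not give them.** The t-tests are paired; 0.48 and 0.6 are in SDs of the paired difference; 4 participants per sequence; a linear period step of b such SDs per period; withdrawal numbers and intraclass correlation as stated below.

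**1. The plan's own power figures.** Paired t-test, df = 23, noncentrality = effect × √24.
- Effect 0.48: 61.5% two-sided, 73.8% one-sided. Both exceed 60%.
- Effect 0.6: 80.4% two-sided, 88.6% one-sided. The 85% figure is met one-sided only, and 12.3 does not state sidedness.
- Two-sample versions give 22% to 67% and do not fit, so the figures presuppose 24 complete participants analysed as pairs.

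**2. Cost of omitting period.** For either active-sham contrast, the two sessions are one period apart in 4 of the 6 sequences and two apart in 2. The signs cancel across sequences, so there is no bias under balance. The mean squared gap is (4×1 + 2×4)/6 = 2, so the SD of the difference rises by √(1 + 2b²). Simulated power at effect 0.48 (200,000 trials per cell):

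| b | SD factor | t-test, two-sided | t-test, one-sided | condition + period model, two-sided |
|---|---|---|---|---|
| 0 | 1.00 | 61.5% | 73.8% | 63.3% |
| 0.1 | 1.01 | 60.6% | 73.2% | 63.2% |
| 0.2 | 1.04 | 58.4% | 71.6% | 63.3% |
| 0.3 | 1.09 | 54.7% | 68.8% | 63.4% |
| 0.5 | 1.22 | 43.3% | 59.8% | 63.3% |

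The t-test's loss at b = 0.1 is 61.5 − 60.6 = 0.9 point two-sided and 73.8 − 73.2 = 0.6 one-sided. At b = 0.3 it is 6.8 and 5.0. The t-test's two-sided size falls from 5.1% at b = 0 to 3.4% at 0.3 and 1.7% at 0.5. The model's lead at b = 0 comes from 44 residual df under equal variances, not from adjusting for period. Regressing the paired difference on period (21 df) gives 61.1% to 61.2% at every b, so it costs 61.5 − 61.1 = 0.4 point when there is no trend.

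**3. Information lost by exclusion.** After two stimulated sessions, S-At and At-S leavers hold a sham/theta-gamma pair, S-Ad and Ad-S leavers hold a sham/delta-beta pair, and At-Ad and Ad-At leavers hold none. A sham-active pair is therefore lost in 4 of 6 sequences, 2 of 6 per contrast. Nobody who leaves after one session has a pair. Adding two leavers with two sessions each to 24 completers (generalised least squares, random participant intercept, condition and period fixed) cuts contrast variance by 4.2% on average at intraclass correlation 0.5, with a range of 2.4% to 7.7% by sequence. The average is 4.5% at correlation 0.3 and 3.9% at 0.9. Two leavers with one session each give 1.3% at 0.5.

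**4. Completer selection.** The completer mean minus the all-randomised mean equals dropout share × gap in mean effect between completers and leavers. For assumed shares of 5% to 20% and gaps of 0.25 to 1.0 SD, this runs from 0.05 × 0.25 ≈ 0.01 SD to 0.20 × 1.0 = 0.20 SD. The documents give neither input, so this is a range and not an estimate of the bias.

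**5. What a withdrawal report would add.** With 24 completers and an assumed 1, 3 or 6 leavers, the rate is 1/25 = 4%, 3/27 = 11% or 6/30 = 20%. The exact 95% intervals are 0.1–20.4%, 2.4–29.2% and 7.7–38.6%. A next study needing 37 completers (80% two-sided power at 0.48) would enrol 37/(1 − rate) = 39, 42 or 47.

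**The case against.** The case for leaving the plan alone has weight. Section 4.1.1 says the unblinded team member "will randomize 24 6-digit stimulation codes", and giving a leaver's code to the next participant tends to keep sequences balanced. Under balance the t-tests are unbiased. Part of the need for a period term arises only once leavers' early sessions are kept. The unstimulated first session probably absorbs much of any practice effect. The behaviour tests concern a within-session contrast (set-size or abstraction), so a uniform practice gain cancels; large b is therefore unlikely there. Sections 2.3 and 9.2 report few and mild side effects, so discomfort withdrawals may be rare. All of this stands, and it limits the size of the gain. It does not justify discarding completed pairs when the alternative costs so little.

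A reader might go further in three ways that the documents do not support.
- **That the primary tests are invalid without a period term.** They are not; under balance they err towards conservatism.
- **That coupling could be tested against the unstimulated first session and so be confounded with time.** The coupling tests name no comparator, and 7.2 does use "the strength of phase amplitude coupling in the baseline session", but only for a secondary brain-behaviour correlation. Section 12.1 frames its null, for performance, relative to sham, and section 4 calls the trial sham-controlled. No section makes session 1 a primary comparator, so this needs only a clarifying phrase.
- **That withdrawals will be concealed.** Section 4.1.2 concerns the final analysis. Section 10.3.2 keeps safety data and notes to file, and 12.2 is silent on reporting withdrawals without ruling it out.

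**Conclusion.** The point holds as a low-cost improvement that should be made. The stated rules restrict the effect and Aim 3 estimates to completers, discard usable within-person contrasts, and leave any period trend in the error term. The expected gain is modest: negligible power at a trend of 0.1 SD per period, a worthwhile amount at 0.3 SD, and about 4% of variance from two retained leavers. These figures rest on an assumed trend, balance and intraclass correlation. The size of any completer selection cannot be determined from the documents. The sponsor already plans a model of the required form, so the change is mainly one of making it primary. The visit wording, comparator, sidedness and withdrawal report are clarifications that can be made in the same edit; the point does not depend on them.

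**What to change.** **Section 4.1.2.** Keep all usable stimulated sessions of every randomised participant in the analysis, even when a replacement is enrolled. Define a usable session before unblinding, for example by number of completed blocks. Reconcile the two-visit wording here and in 3.3.2 with the three stimulated sessions in 6.2, 8.4 and Appendix A.

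**Section 12.2.**
- For each outcome, make the primary analysis a linear mixed model on the three stimulated sessions, with condition and period fixed and participant random. For behaviour, model the per-session set-size or abstraction effect.
- If equal variances across conditions are doubted, regress the paired difference on period instead.
- Give completers-only paired t-tests as a sensitivity analysis.
- State that both coupling contrasts are active minus sham, one-sided as planned, and give the sidedness of the behaviour tests.
- Report withdrawals by condition and reason, with the rate and its confidence interval.

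**Cost.** Edits to two sections (plus the 3.3.2 wording) and slightly more analysis; no new visits or data, since withdrawals are already noted to file. The mixed model assumes equal variances across conditions; the paired-difference version avoids that at about 0.4 point of power. Neither fully corrects selection, because someone who leaves before giving both a sham and an active session adds little or nothing to the contrast.

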3 SUBJECT SELECTION AND WITHDRAWAL

A total of 24 participants will be recruited for this study and all data will be collected at UNC-CH. No specific plans have been made to enroll participants from vulnerable populations.

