5.2 STIMULATION SESSIONS

Participants will undergo four sessions with the same procedure; the only change will be the stimulation condition. In the initial session, participants will have the procedure explained and reminded of their expectations and rights (informed consent). After obtaining consent, a urine drug test and pregnancy screening will be administered. Sessions 2, 3, and 4 will be the same as session 1, except there will be no CF-tACS stimulation during session 1.

5.4.1 SESSION 1

In the initial session, participants will be explained the procedure and reminded of their expectations and rights (informed consent). After obtaining consent, a urine drug test and pregnancy screening will be administered.

- Preparation - Once a negative pregnancy test and negative drug test are confirmed, the stimulation electrodes, EEG net, ECG electrodes and respiration belt will be applied.
- Questionnaires - The participant will fill out a series of questionnaires pertaining to self-reported handedness, affect, behavioral traits and sleep quality.
- Saliva collection - Saliva will be collected for BDNF genotyping and sex hormone level measurement.
- Resting state EEG – Participant will be asked to relax with eyes open and EEG will be collected simultaneously
- Practice cognitive tasks - The participant will perform a shortened version of the cognitive tasks as practice from which baseline performance will be assessed.

· Following the practice, the participant will receive 40 minutes of either verum CF-tACS or sham CF-tACS stimulation, depending on the randomized condition. During the stimulation, the following procedures will be followed

A. Cognitive Control Task – Participant will perform a cognitive control task for 5 minutes. CF-tACS will be delivered during these 5 minutes. There will be no CF-tACS during session 1.

B. Resting state EEG - Participant will be asked to relax with eyes open and EEG will be collected simultaneously for 3 minutes. There will be no CF-tACS during this time. Subject are allowed to take more (but not less) than 3 minutes of rest if desired.

- Repeat steps A and B 8 times until all conditions of the Cognitive Control Task are finished

Following the end of stimulation,

- Electrodes and net will be removed and participant can wash their hair and face

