6.2 SPECIAL ASSAYS OR PROCEDURES

Each participant will receive stimulation on three days, separated by a week. Two sessions will involve verum CF-tACS, and the other will involve sham tACS; the order of stimulation condition will be randomized for each participant. For more information on the stimulation procedures, see section 8.2 *Preparation and Administration of Study Investigational Product*.

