10.3 EARLY WITHDRAWAL OF PARTICIPANTS

10.3.1 REASONS FOR WITHDRAWAL

A study participant will be discontinued from further participation if:

- The participant fails to adhere to rules, including stress, exercise, and sleep restrictions

- The participant meets any exclusion criteria (either newly developed or not previously recognized).
- Anything that, in the opinion of the investigator, would place the participant at increased risk or preclude the participant's full compliance with or completion of the study.
- Participants experience severe discomfort during stimulation

Participants are free to withdraw from participation in the study at any time upon request.

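### Section 4.1.2 reissues a dropout's stimulation codes to the next participants, which creates an avoidable risk of partial unblinding for replacements

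*Combined protocol and SAP*

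**What the plan says.** All references are to the combined protocol and SAP.

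- **Reuse.** For a dropout, section 4.1.2 states that "data will not be included in the final analysis and the stimulation codes will be reused for the next participants".
- **What a code is.** Section 4.1.1 provides "24 6-digit stimulation codes which will be used by the study coordinator and research assistants". It ties these codes both to participant numbers and to the treatment given at each session. The code sheet in the same section carries the entry "Stimulation code: 6-digit numerical code for the stimulation session", next to a condition number and a condition name.
- **What is concealed.** Staff receive the code sheet without the condition columns. The code-holder takes no part in data collection or analysis (4.1.1), and the link from code to waveform is hidden from the experimenter (8.3).
- **What staff see.** The coordinator or a research assistant attends every stimulation session (8.3). The same roles check on the participant during stimulation and discuss side effects rated moderate or severe (9.3).
- **Withdrawal.** The reasons in section 10.3.1 include "Participants experience severe discomfort during stimulation", and section 9.3 also withdraws a participant who rates discomfort as severe.

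**The concern.** Hiding the code-to-treatment key protects the blind only while a code means nothing to the people who use it. Once staff have watched a participant under a code, and perhaps discussed marked side effects with that person, the code has a history. The staff copy of the code sheet still shows identifiers and codes, so a reissue can be seen without relying on memory. The replacement then starts with staff who may already lean towards verum or sham for a given session.

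Reaction time and accuracy are among the primary outcomes (7.1) and are collected with those staff present. The side-effects questionnaire comes after each stimulation session. The documents describe no blinding check, such as a treatment guess, so leakage would not be detected. They also give no reason for reusing the code itself. Keeping the sequences balanced needs only the same sequence, not the same code.

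**Working it through.** **Inputs**
- Participants: 24 (section 3: "A total of 24 participants will be recruited for this study").
- Stimulated sessions per participant: 3 (section 6.2: "Each participant will receive stimulation on three days, separated by a week"). Section 5.2 makes the later sessions like the first, "except there will be no CF-tACS stimulation during session 1", and Appendix A agrees. One line in the session 1 description reads as if stimulation were given at that visit. Those passages must be reconciled; the count here uses three.
- Codes: 24 (4.1.1). Treatment sequences: 6 (section 4).
- Dropout rate *d*: not in the documents. Assumed, with a range shown.

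**Step 1: the plan's figure of 24 codes**
- One code per participant: 24 × 1 = 24. This reproduces the stated number, with 24 / 6 = 4 codes per sequence. A code recurs over its holder's three sessions but stands for a different treatment each time.
- One code per session: 24 × 3 = 72. The stated number would be 72 − 24 = 48 short. Each code would be used 72 / 24 = 3 times on average, and 48 / 72 = 67% of uses would be on a code already seen.

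Section 4.1.1 has wording for both readings, so the unit of a code is not settled.

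**Step 2: how many participants reuse could touch**

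Assume each code's first holder drops out independently with probability *d*, and every dropout is replaced.

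| Assumed *d* | Final participants on a reissued code, 24*d* | Chance of at least one, 1 − (1 − *d*)^24 | Total reissues, 24*d*/(1 − *d*) |
|---|---|---|---|
| 5% | 1.2 | 71% | 1.3 |
| 10% | 2.4 | 92% | 2.7 |
| 20% | 4.8 | 99.5% | 6.0 |
| 25% | 6.0 | 99.9% | 8.0 |

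**Step 3: why these counts are upper limits**

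They treat every dropout as having been stimulated. Sequences are assigned at the first visit (section 4), while stimulation starts at session 2. Someone lost in between leaves a code that nobody has seen in use. Someone lost after one stimulated session exposes at most one of three sessions.

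**Step 4: how strong the hint can be**

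Two of the three conditions are verum, so before any evidence a session is verum with probability 2/3. Side effects shift this by the ratio of their frequency under verum to that under sham, which the documents do not give. Verum lasts 8 × (300 + 10 + 10) = 2,560 seconds. Sham lasts 80 seconds in section 4 and 40 seconds in section 8.3, two figures that must be reconciled. The ratio of durations is 2,560 / 80 = 32 or 2,560 / 40 = 64. That makes a hint of verum versus sham plausible, but does not measure it. Nothing here separates theta-gamma from delta-beta.

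**The case against.** The blind has real protection. The key is hidden, the code-holder is independent, and sham delivers brief real stimulation that section 4 says participants can generally not tell from none. Many dropouts would carry no side-effect information: sections 8.4 and 10.3.1 also list missed sessions, broken study rules, newly met exclusions and voluntary withdrawal. Section 2.3 reports no significant side effects in the laboratory's earlier 40-minute studies. The individual who meets a reissued code need not be the one who saw it first, since 8.3 names roles and gives no team size.

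All of this limits the size of the risk. None of it removes the route, because no section gives a replacement a new code.

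A reader might go further and infer that 24 codes cannot cover 72 sessions. That follows only if a code belongs to one session. The link to participant numbers and the exact match with 24 participants fit one code per participant equally well, so the documents show an ambiguity and not a shortage.

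A reader might also infer that reuse follows mostly from discomfort, or that code-handling staff influence task performance or EEG cleaning. The documents do not give the mix of dropout reasons, do not say that staff coach participants, and do not say who runs the EEG preprocessing.

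**Conclusion.** The point holds as an avoidable risk of partial unblinding. It concerns replacement participants only, and only sessions their predecessor had already received. The information that leaks is a probabilistic hint of verum versus sham. At an assumed dropout of 10% to 20%, the expected number affected is at most about 2 to 5 of 24, and lower if some dropouts leave before stimulation. The result rests on dropouts being replaced as 4.1.2 describes and on some overlap between the staff who saw the first holder and those who run the second. It would be too strong to conclude that the double blind as a whole is undermined: the treatment key stays concealed, and participants on first-issue codes are not touched by reuse. Separately, section 4.1.1 leaves the unit of a code undefined and should settle it.

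**What to change.** In section 4.1.2, replace the reuse rule with: *The unblinded code-holder assigns the replacement participant to the same treatment sequence under new, never-issued codes; no code is reissued to another participant, and staff are not told which dropout a participant replaces.* The last clause is needed because staff who know who replaces whom can carry the same guess across under any code. The dropout definition in 4.1.2 also speaks as if there were two visits and should be aligned with the three stimulation sessions.

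In section 4.1.1, state whether a code belongs to a participant (a sequence) or to a single session.
- Per participant: 24 codes plus one per replacement, about 24 + 2.7 = 26.7 at 10% dropout and 24 + 6 = 30 at 20%.
- Per session: 72 unique codes plus spares, three per replacement, or about 3 × 2.7 = 8 to 3 × 6 = 18.

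The cost is a few extra codes and minutes of work for the existing code-holder. Sample size, visits and analysis do not change.
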